## **5.3 Lifestyle Considerations**

### **5.3.1 Meals and Dietary Restrictions**

To properly evaluate the efficacy and safety of ETC-1002, diet therapy receiving since before informed consent should not be changed from Week -2 to the end of tests at Week 52 (or to the completion of the assessments at Discontinuation Visit, if applicable) in principle. For dietary supplements that may affect cholesterol levels including LDL-C, the investigator or subinvestigator will explain to the subjects at each visit so that the intake status will not change from Week -2 to the end of the tests at Week 52 (or to the completion of the assessments at Discontinuation Visit, if applicable), and record the intake status in the source document.

### **5.3.2 Caffeine, Alcohol, and Tobacco**

For alcohol and tobacco, the usual amount of alcohol consumed and the number of cigarettes smoked prior to participation in the trial will be checked with the subject and documented in the source document. The investigator or subinvestigator will instruct subjects not to significantly increase the amount of alcohol consumption or the number of cigarettes smoked during the trial period. Subjects will be monitored at each visit for any significant changes from Week -2 to the end of the tests at Week 52 (or to the completion of the assessments at Discontinuation Visit, if applicable), and the results will be recorded in the source document. No caffeine restrictions will be applied.

### **5.3.3 Activity**

To properly evaluate the efficacy and safety of ETC-1002, exercise therapy that has been received since before informed consent should not be changed during the trial period to the extent possible. In addition, the investigator or subinvestigator will instruct subjects at each visit to refrain from strenuous exercise from approximately 1 week before the scheduled visits during the trial period to avoid influence on laboratory values such as CK.

## **5.4 Screen Failures**

A screen failure is a subject from whom informed consent is obtained and is documented in writing (ie, subject signs an ICF), but who does not receive the IMP in the treatment period regardless of a newly enrolled subject or a rollover subject from the phase 3 confirmatory trial (Protocol No. 346-102-00002). All AEs must be reported after subject informed consent has been obtained, including screening failures due to AEs, irrespective of IMP administration. If the subject meets the definition of a screen failure in this trial, the following information will be recorded in the eCRF:

- Date of informed consent
- Visit date (screening visit)
- Demographics (collection date, birth date, sex, race, ethnicity, country)
- History of hypercholesterolemia

History of Hypercholesterolemia: Investigation Item

• Name of diagnosis

• Date of diagnosis

• Presence or absence of familial hypercholesterolemia

• Classification and details of classification (according to the flowchart using the Suita score in the Japan Atherosclerosis Society Guidelines for Prevention of Atherosclerotic Cardiovascular Diseases 2017, and according to the flowchart using the score of the Hisayama Study in the Guidelines 2022)

• Statin response (inadequate response to statins/difficulties in treatment with statins)

• For patients with difficulties in treatment with statins: Reasons for judging that treatment with statins is difficult and the name/daily dose of the statin

- Result of eligibility assessment
- Screen failure date
- Reason for screen failure
- Adverse events\*

\*If a rollover subject from Trial 346-102-00002 is a screen failure, no AE collection will be necessary on the eCRF in this trial.

Screen failures will be allowed to re-screen. In the event that the subject is re-screened for trial participation, a new ICF must be signed.

## **6 Trial Treatments**

Trial intervention used in this trial is a test product. No trial interventions are used in this trial other than the IMP.

### **6.1 Trial Treatments Administered**

Subjects who are judged to be eligible at screening will proceed to the treatment period. Subjects proceeding to the treatment period who have been receiving treatment using lipid-lowering drugs since before informed consent should continue the treatment without changing the type or dose and regimen, in addition to orally receiving ETC-1002 at 180 mg once daily. The time of IMP administration should be same to the extent possible. The following information will be recorded in the eCRF: for the IMP, the number of tablets taken per day, start and end dates of administration; for lipid-lowering drugs, the name of the drug, route of administration, dose and frequency, daily dose, start and end dates of administration.

No change in the dose of lipid-lowering drugs is allowed in principle during the trial. However, if the lipid management target in the Japan Atherosclerosis Society Guidelines for Prevention of Atherosclerotic Cardiovascular Diseases (2017) are not achieved on and after Week 12, and if the investigator or subinvestigator considers that further treatment is necessary and there are no safety problems, starting a dose increase or concomitant treatment with other lipid-lowering drugs will be permitted.

For information regarding the dose regimen and treatment period (including the post-treatment follow-up period), see [Section 4.1](#).

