### **3 Objectives and Endpoints**

The objectives and endpoints of this trial are shown in Table 3-1.

Table 3-1 Trial Objectives and Endpoints	
Objectives	Endpoints
Primary Objective: 
 
To assess the safety of ETC-1002 at 180 mg administered for 52 weeks in patients with hyper-LDL cholesterolemia
 
	Safety Assessments: 
 
Adverse events, clinical laboratory tests, vital signs (blood pressure, pulse rate, and body temperature), body weight, physical examination, and 12-lead ECG
 

Secondary Objectives: 
 
To assess the effects of ETC-1002 at 180 mg administered for 52 weeks on LDL-C in patients with hyper-LDL cholesterolemia
 
To assess the effects of ETC-1002 on non-high-density lipoprotein-cholesterol (non-HDL-C), total cholesterol (TC), apolipoprotein B (apo B), high-sensitivity C-reactive protein (hsCRP), and glycosylated hemoglobin (HbA1c)
 
	Efficacy Assessments: 
 
Percent change in low-density lipoprotein cholesterol (LDL-C) from baseline to Week 52
 
Percent change in non-HDL-C, TC, apo B, hsCRP, and HbA1c from baseline to Week 52
 
Proportion of subjects whose LDL-C value achieves the lipid management goals based on the risk assessment (<100 mg/dL [history of coronary artery disease or heterozygous familial hypercholesterolemia], <120 mg/dL [high risk], or <140 mg/dL [intermediate risk]) at Week 52
 

Other Efficacy Assessments: 
 
To assess the effects of ETC-1002 at 180 mg administered for 52 weeks on HDL-C and triglycerides (TG) in patients with hyper-LDL cholesterolemia
 
	Other Efficacy Assessments: 
 
Percent change in HDL-C and TG from baseline to Week 52
 

[Section 9.4](#) describes the statistical analysis of the endpoints.

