3.2 Trial Treatments

Subjects who proceed to the treatment period will orally receive ETC-1002 180-mg tablets once daily for 52 weeks. Administration of lipid-lowering drugs used before informed consent should be continued without changing the type or dose and regimen.

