5.3 Handling of Missing Data

Missing data will not be imputed.

Fasting lipid parameters will be handled as shown in the table below with regard to fasting conditions.

Fasting Lipid Parameters	Handling of Data
LDL-C (direct method)	Parameter to be used in the analysis, irrespective of fasting conditions
non-HDL-C, TC, HDL-C, TG, LDL-C (Friedewald formula)	Parameters to be used in the analysis only when obtained under fasting conditions

6 Primary and Secondary Outcome Variables

There are no primary or secondary outcome variables.

7 Disposition and Demographic Analysis

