7.4 Treatment Compliance

For each analysis set, frequency distributions of the IMP compliance rate (<70%, ≥70% to <80%, ≥80% to <90%, or ≥90%) in the treatment period will be summarized by rollover, newly enrolled, and overall subjects. The IMP compliance rate will be calculated using the following formula.

$$\text{IMP compliance rate (\%)} = \frac{\text{Actual number of days taking the IMP}}{\text{Date of last IMP administration} - \text{Date of initial IMP administration} + 1} \times 100$$

The same analysis will be performed for each statin response.

For each analysis set, the number and percentage of subjects who do not change the type and dosage regimen of lipid-lowering drugs, which are mandatory concomitant medications in this trial, throughout the treatment period will be summarized by rollover, newly enrolled, and overall subjects.

The same analysis will be performed for each statin response.

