8.1 Efficacy Endpoints

Descriptive statistics of the actual value, change from baseline, and percent change from baseline will be calculated at each time point for LDL-C (direct method). In addition to the summarization at each time point, summarization at the Last Visit will also be performed.

Descriptive statistics of the actual value, change from baseline, and percent change from baseline will be calculated at each time point for non-HDL-C, TC, apo B, hsCRP, and HbA1c. The analysis visits for apo B, hsCRP, and HbA1c will be Weeks 12, 24, 36, and 52.

The number and percentage of subjects whose LDL-C values achieve the lipid management goal based on the risk assessment (<100 mg/dL [history of coronary artery disease or heterozygous familial hypercholesterolemia], <120 mg/dL [high risk], or <140 mg/dL [intermediate risk]) will be calculated at each time point.

The time course of the mean \pm standard deviation for the percent change from baseline in the efficacy endpoints will be plotted.

The same analysis will be performed for each statin response.

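### Lipid-lowering therapy may be intensified from Week 12 in subjects not at goal, but the SAP summarises later lipids and goal attainment without regard to it, so added-drug effect is mixed with ETC-1002.

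*Protocol*

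**What the plan says.** **Objective.** Protocol Section 3 lists as a secondary objective "To assess the effects of ETC-1002 at 180 mg administered for 52 weeks on LDL-C in patients with hyper-LDL cholesterolemia". The endpoints include percent change in LDL-C, non-HDL-C, TC and apo B to Week 52, and the proportion at the LDL-C goal at Week 52.

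**Background therapy.** SAP 3.2 states: "Administration of lipid-lowering drugs used before informed consent should be continued without changing the type or dose and regimen". SAP 3.1 and the opening of Protocol 6.5.3 say the same in substance. Protocol 6.1, and a later paragraph of 6.5.3, make an exception. If the lipid goals "are not achieved on and after Week 12, and if the investigator or subinvestigator considers that further treatment is necessary", and there is no safety problem, then "starting a dose increase or concomitant treatment with other lipid-lowering drugs will be permitted".

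**Analysis.**
- SAP 8.1 calls for descriptive statistics at each visit for LDL-C (direct method) and the other lipids, and for the number and percentage at goal at each visit. It states no denominator for that percentage.
- SAP 3.4 removes only values taken more than 2 days after the last IMP dose.
- SAP 5.3 adds: "Missing data will not be imputed".
- SAP 8.3 lists subgroups for LDL-C at Weeks 24 and 52. None is defined by a change in background therapy.
- SAP 7.4 tabulates "subjects who do not change the type and dosage regimen of lipid-lowering drugs", but nothing in the efficacy section uses that classification.
- SAP 8.1 also plans a Last Visit summary for LDL-C (direct method).

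**The concern.** Intensification is not random noise in the background therapy. It is open only to subjects who have missed the goal, and in substance that is the goal the attainment endpoint later scores. A subject who receives an added drug and then reaches goal is counted as a success in a table meant to describe ETC-1002. The same subject's later LDL-C, non-HDL-C, TC and apo B carry the effect of both treatments.

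A control arm under the same rule would let a reader judge how much came from the added drugs. This trial has none. Persistence of effect to Week 52 is the efficacy question that a 52-week trial is placed to answer, and a waning ETC-1002 effect could be masked by gradual intensification. Visits before Week 12 are unaffected, and the Week 12 window (Days 72-99) largely so. The problem lies in the later visits, including Week 52.

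**Working it through.** **The plan's own figure.** Protocol 9.1 sets 120 subjects so that 100 complete, with about 20 withdrawals. 100 + 20 = 120, and 100 / (1 - 20/120) = 120. It reproduces, and nothing below changes it.

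**Inputs.** The Japanese phase 2 trial gives m = -21.26% for LDL-C at Week 12 on 180 mg (Protocol 2.1). The documents do not give the share intensified (f), the extra relative LDL-C reduction (r), the share of intensified subjects who then reach goal (c), or the share at goal without intensification (g). These are assumed.

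**Could many subjects qualify?** A subject who falls by exactly 21.26% keeps 78.74% of baseline. The goal is then missed if baseline is above about 100/0.7874 = 127.0, 120/0.7874 = 152.4 or 140/0.7874 = 177.8 mg/dL, by risk category. Entry requires only values at or above 100, 120 or 140 mg/dL, so baseline alone does not make eligibility for intensification rare or universal.

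**Mean percent change.** If intensified subjects would otherwise have the average change, the shift is -f x r x (100 + m) = -f x r x 78.74 points:

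| f | r = 10% | r = 20% | r = 30% |
|---|---|---|---|
| 10% | -0.8 | -1.6 | -2.4 |
| 20% | -1.6 | -3.1 | -4.7 |
| 30% | -2.4 | -4.7 | -7.1 |

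A Week 52 mean of -21.26% on ETC-1002 alone would read between -22.0% and -28.3%. For rollover subjects who already took ETC-1002 in the confirmatory trial (an assumption, since its arms are not described), baseline is taken on drug and m may be near 0. The shift is then -f x r x 100, or -1 to -9 points.

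**Goal attainment.** The observed share is g + f x c, if intensified subjects would otherwise have stayed above goal. The increase runs from 0.10 x 0.30 = 3 points to 0.30 x 0.70 = 21 points. With g = 40%, the table would show 43% to 61%.

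**Withdrawals and the denominator.** Suppose 40 of 100 subjects with Week 52 data are at goal. Observed cases gives 40%. With 120 as denominator the figure is 40/120 = 33.3% if none of the 20 withdrawals was at goal, 48/120 = 40% if 8 were, and 60/120 = 50% if all were. The direction depends on a quantity the documents do not give.

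**Does setting post-intensification values to missing repair the mean?** Take a true ETC-1002-only mean of -21.26%, 20% intensified with an own change of -5%, and a 25% added effect.
- Subjects not intensified: (-21.26 + 0.2 x 5) / 0.8 = -25.3%. This is what the censored mean shows.
- Intensified subjects as observed: 95 x 0.75 = 71.25, a change of -28.75%. The all-data mean is 0.8 x (-25.325) + 0.2 x (-28.75) = -26.0%.

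Censoring recovers only 0.7 of the 4.7 points. With an own change of -15%, the two means are -22.8% and -25.5%. Carrying forward the last pre-intensification value returns -21.26% in both cases, provided that value equals what the subject would have had at Week 52 without added drugs.

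**The case against.** The strongest reply is that efficacy here is supportive. The primary objective and the sample size rest on long-term safety, SAP 6 says there are no primary or secondary outcome variables, and no test or error rate is involved. That stands, and it limits the severity.

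The plan is also partly transparent. SAP 7.4 counts subjects with unchanged therapy, listings show individual lipid-drug use and LDL-C, and early visits are reported separately. That stands too, but counts and listings do not show what Week 52 would look like without the added drugs.

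Intensification may be uncommon. Background doses are fixed in principle, and the exception needs a missed goal, a judgement that treatment is necessary and no safety problem. This is fair, and it is why the magnitudes above are only illustrations.

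Two stronger readings are tempting. A reader might infer that missing data also flatter the results, because withdrawals leave the Week 52 percentage. The documents do not support a direction: a subject who stops for an adverse event may well have been at goal. Nor do all LDL-C summaries lose withdrawals, since the Last Visit summary for LDL-C (direct method) keeps their last on-treatment value. That summary still includes post-intensification values, and SAP 8.1 states none for attainment. A reader might also infer that discarding post-intensification values is the natural headline analysis. It drops subjects selected for missing the goal, and the calculation shows that it can leave most of the distortion in place.

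**Conclusion.** The concern holds for intensification. As written, the SAP attributes the effect of permitted added drugs to ETC-1002 in the post-Week-12 lipid and attainment summaries, and the distortion is expected to be favourable. About 1 to 7 points on mean LDL-C and 3 to 21 points on attainment follow from the assumed ranges; neither is an estimate for this trial.

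The goal-attainment denominator is a separate, smaller gap. It is not stated, observed cases is the natural reading of no imputation, and the direction of any effect is unknown.

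This should be fixed. It does not affect the primary safety objective, the sample size or any inferential claim. It does limit how far the 52-week efficacy figures can be read as effects of ETC-1002.

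**What to change.** In SAP 8.1:

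1. Add a goal-attainment analysis by visit with the efficacy analysis set as denominator. Count a subject with prior intensification, or with no value at that visit, as not achieving. Show it beside the observed-case percentage, with that denominator stated. Missing-as-not-achieving is a convention and should be labelled as one.
2. For LDL-C, non-HDL-C, TC and apo B, keep the all-data summary and add one that carries the last pre-intensification value forward for intensified subjects. Define intensification as the first lipid-lowering dose increase or addition after Day 1. Do not make simple censoring the sole headline.
3. Report the number and timing of intensifications by visit, for rollover, newly enrolled and overall subjects.
4. Reconcile the wording on unchanged background therapy in SAP 3.1 and 3.2, and the opening of Protocol 6.5.3, with the allowance in Protocol 6.1 and 6.5.3. The clinical rule itself is not in question.

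Cost: SAP wording and a few tables. Protocol 6.1 already has drug, dose and start and end dates recorded in the eCRF. The added lipid summary rests on a carried-forward assumption and may be slightly conservative, because a value that prompts intensification may be high partly by chance. The added attainment figure will be somewhat less favourable.

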#### **6.1.1 Medical Devices**

Not applicable.

### **6.2 Management of Investigational Medicinal Product**

For full details on IMP management, please refer to the IB and the separate procedures.

### **6.2.1 Packaging and Labeling**

The IMP will be provided by the sponsor or designated agent to the IMP storage manager. The IMP will be supplied as blister cards. Each blister card used in the dosing period will be labeled to clearly disclose the compound ID, trial number, sponsor's name and address, storage temperature, route of administration, appropriate precautionary statements, etc.

### **6.2.2 Storage**

The IMP will be stored in a securely locked cabinet or enclosure. Access will be limited to the IMP storage manager.

The IMP will be stored according to the conditions indicated on the IMP label.

The trial site staff will maintain a temperature log in the IMP storage area to record the temperature.

### **6.2.3 Accountability**

The IMP storage manager must maintain an inventory record of IMP (test product) received, dispensed, administered, and returned. The IMP storage manager must not provide IMP to any subject not participating in this protocol.

### **6.2.4 Returns and Destruction**

Upon completion or termination of the trial, all unused IMP and partially used IMP must be returned to the sponsor or a designated agent. All IMP returned to the sponsor must be accompanied by inventory record, etc. and be clearly identified by protocol number and trial site number on the outermost shipping container. Returned supplies should be in the original containers. The assigned trial monitor will facilitate the return of used IMP containers, unused IMP, and partially-used IMP.

### **6.2.5 Reporting of Product Quality Complaints**

A Product Quality Complaint (PQC) is any written, electronic, or oral communication provided by a healthcare professional, consumer, subject, medical representative, regulatory agency, Partner, or other third party that alleges deficiencies related to the

identity, quality, durability, reliability, safety, effectiveness, or performance of a Medical Device or Medicinal Product or a falsified, tampered, or diverted product after it is released for distribution to a clinical trial. Examples include, but are not limited to:

- Failure/malfunction of IMPs to meet any of its specifications
- Incorrect or missing labeling
- Packaging issues (eg, damaged, dirty, crushed, missing product)
- Blister defects (eg, missing, empty blisters)
- Product defects (eg, odor, chipped, broken, embossing illegible)
- Loss or theft of the product

#### **6.2.5.1 Eliciting and Reporting Product Quality Complaints**

The investigator, subinvestigator, or designee must record each PQC identified through any means from the receipt of the IMP from the sponsor or sponsor's designee, through and including reconciliation and up to destruction, including subject dosing. The investigator, subinvestigator, or designee must notify the sponsor (or sponsor's designee) by e-mail [REDACTED] of the information specified in [Section 6.2.5.2](#) immediately after becoming aware of the PQC.

Identification of a PQC by the subject should be reported to the site investigator or subinvestigator, who should then follow the reporting procedure above.

#### **6.2.5.2 Information Required for Reporting Product Quality Complaints**

- Description of the complaint
- Reporter identification (eg, subject, investigator, subinvestigator, trial site, etc.)
- Reporter contact information (eg, address, phone number, e-mail address)
- ID of the material (product/compound name, kit number)
- Clinical protocol reference (protocol number and/or trial name)
- Dosage form/strength (if known)
- Pictures of complaint sample (if available)
- Availability of the complaint sample for return

#### **6.2.5.3 Return Process in Case of Product Quality Complaints**

Indicate during the report of the PQC if the complaint sample is available for return. If the complaint sample is available for return, the sponsor will provide return instructions, when applicable.

It must be documented in the site accountability record that the complaint sample has been forwarded to the sponsor for complaint investigation.

#### **6.2.5.4 Assessment/Evaluation**

Assessment and evaluation of PQC's will be handled by the sponsor.

#### **6.2.6 Investigational Medicinal Product Reserve Sample Requirements**

Not applicable.

### **6.3 Measures to Minimize/Avoid Bias**

This is an open-label trial.

### **6.4 Subject Compliance**

To ensure compliance with the protocol, the investigator or subinvestigator will instruct subjects to:

- Visit the trial site in a fasting state (fasting for at least 10 hours) without taking the IMP on the days specified in the protocol.
- Not take any prohibited concomitant medications or therapies during the period from informed consent to the completion of the tests at Week 52 or to the completion of the assessments at Discontinuation Visit.
- Comply with the dosage regimen, duration, and frequency of administration of the IMP and, if any, concomitant lipid-lowering drugs taken since before informed consent.
- Use appropriate contraceptive methods.
- Note the lifestyle considerations (see [Section 5.3](#)).
- Fill in the subject diary (see [Section 8.10.1](#)) every day while taking the IMP, and bring it to the visit.

